**Table 3: Pembrolizumab 3 weekly schedule and disease assessment timings**

Year 1, First 6 months*									
Week Number:	1	4	7	10	13	16	19	22	25
Start of month:	1				4				7
Pembrolizumab cycle:	1	2	3	4	5	6	7	8	9
Disease Assessment / Scan (+/- 7 days):	Scanned at screening			X			X		
Year 1, Second 6 months*									
Week Number:	28	31	34	37	40	43	46	49	52
Start of month:				10				13	
Pembrolizumab cycle:	10	11	12	13	14	15	16	17	18
Disease Assessment / Scan (+/- 7 days):	X			X			X		
Year 2, First 6 months*									
Week Number:	55	58	61	64	67	70	73	76	79
Start of month:			16				19		
Pembrolizumab cycle:	19	20	21	22	23	24	25	26	27
Disease Assessment / Scan (+/- 7 days):		X				X			
Year 2, Second 6 months*									
Week Number:	82	85	88	91	94	97	100	103	106
Start of month:		22				25			
Pembrolizumab cycle:	28	29	30	31	32	33	34	35	Stop
Disease Assessment / Scan	X				X				X

(+/- 7 days):

\*A month is 4 weeks (not a calendar month).

Table 4: Schedule of Study Assessments – Year 1

	Screening	Cycle 1 (21-d cycle)							Cycle Number – Year 1														Post Treatment Visit  +30 from last dose	Follow Up 	
		2	3	4	5	6	7	8	9	10	11	12	13	14	15	16	17	1 	1 						
Day	Up to -28	1	2	3	4	8	15	22	43	64	1 	1 	1 												
Start of Week # (+/- 3 days)	-4 weeks to 0		1		2	3	4	7	10	13	16	19	22	25	28	31	34	37	40	43	46	49			
Demographics 	X																								
Medical history	X																								
Inclusion/exclusion checks	X																								
Pregnancy or FSH test 	X							X	X	X	X	X	X	X	X	X	X	X	X	X	X	X	X	X	
ECOG PS	X							X	X	X	X	X	X	X	X	X	X	X	X	X	X	X	X	X	
Vital signs 	X	X	X	X	X	X	X	X	X	X	X	X	X	X	X	X	X	X	X	X	X	X	X	X	
Physical examination 	X	X	X	X	X	X	X	X	X	X	X	X	X	X	X	X	X	X	X	X	X	X	X	X	
Clinical chemistry 	X	X	X	X	X	X	X	X	X	X	X	X	X	X	X	X	X	X	X	X	X	X	X	X	
Hematology 	X	X	X	X	X	X	X	X	X	X	X	X	X	X	X	X	X	X	X	X	X	X	X	X	
Coagulation 	X	X				X	X	X	X	X	X	X	X	X	X	X	X	X	X	X	X	X	X	X	
Urinalysis	X	X				X	X	X																	X
Thyroid function tests 	X							X		X		X		X		X		X		X		X		X	X
Echocardiogram (or MUGA) 	X																								X
ECG 	X	X	X	X	X	X	X	X	X	X	X	X	X	X	X	X	X	X	X	X	X	X	X	X	
Tumor imaging 	X																								(X)
Disease Assessment 	X																								(X)
Tumor (fresh tissue) biopsy 	X	(X: up to 2 optional post treatment biopsies)																							
Tumor (archival) 	(X)																								
Biomarkers 	X	(X)			X	X		X	X	X	X	X	X	X	X										
Pembrolizumab dosing 		X						X	X	X	X	X	X	X	X	X	X	X	X	X	X	X	X	X	
BGB324 dosing 			X – consecutive daily dosing in 21-d cycles																						
PK sampling (BGB324) 		X	X	X	X	X	X	X	X	X	X	X	X	X	X	X	X	X	X	X	X	X	X	X	
PK sampling (pembrolizumab) 		X	X	X	X	X	X	X	X	X	X	X	X	X	X	X	X	X	X	X	X	X	X	X	
Adverse events		X	X	X	X	X	X	X	X	X	X	X	X	X	X	X	X	X	X	X	X	X	X	(X)	
Concomitant medication	X	X	X	X	X	X	X	X	X	X	X	X	X	X	X	X	X	X	X	X	X	X	X	(X)	
Subsequent anti-cancer treatment																									X
Survival Follow Up 																									X

Table 5: Schedule of Study Assessments - Year 2

	Cycle Number – Year 2																		Post Treatment Visit 	Follow Up 	
	18	19	20	21	22	23	24	25	26	27	28	29	30	31	32	33	34	35			
Day	1 	1 	1 	1 	1 	1 	1 	1 	1 	1 	1 	1 	1 	1 	1 	1 	1 	+30 from last dose			
Week Number (+/- 3 days)	52	55	58	61	64	67	70	73	76	79	82	85	88	91	94	97	100	103			
Pregnancy test 	X	X	X	X	X	X	X	X	X	X	X	X	X	X	X	X	X	X			
ECOG PS	X	X	X	X	X	X	X	X	X	X	X	X	X	X	X	X	X	X	X	X	
Vital signs 	X	X	X	X	X	X	X	X	X	X	X	X	X	X	X	X	X	X	X	X	
Physical examination 	X	X	X	X	X	X	X	X	X	X	X	X	X	X	X	X	X	X	X	X	
Clinical chemistry 	X	X	X	X	X	X	X	X	X	X	X	X	X	X	X	X	X	X	X	X	
Hematology 	X	X	X	X	X	X	X	X	X	X	X	X	X	X	X	X	X	X	X	X	
Coagulation 	X	X	X	X	X	X	X	X	X	X	X	X	X	X	X	X	X	X	X	X	
Urinalysis																			X		
Thyroid function tests 		X		X		X		X		X		X		X		X		X		X	
Echocardiogram (or MUGA) 								X									X				
ECG 	X	X	X	X	X	X	X	X	X	X	X	X	X	X	X	X	X	X	X	X	
Tumor imaging 			X				X			X				X					(X)	(X)	
Disease Assessment 			X			X			X			X			X			(X)		(X)	
Tumor (fresh tissue) biopsy 																					
Pembrolizumab dosing 	X	X	X	X	X	X	X	X	X	X	X	X	X	X	X	X	X	X	X	X	
BGB324 dosing 																					
Adverse events	X	X	X	X	X	X	X	X	X	X	X	X	X	X	X	X	X	X	(X)		
Concomitant medication	X	X	X	X	X	X	X	X	X	X	X	X	X	X	X	X	X	X	(X)		
Subsequent anti-cancer treatment																				X	
Survival Follow Up 																				X	

**General instructions:**

- Informed Consent must be obtained using the current version of the PIS/ICF prior to commencing Screening.
- From C2 onwards a tolerance window of +/- 3 days is permitted. Other tolerance windows for specific study assessments are described in the footnotes below.
- On dosing days, assessments should be performed prior to dosing unless specified otherwise.
- (X) denotes an optional sample; or a sample which is not taken at every cycle; or the particular assessment is 'if applicable'; X denotes a study visit with multiple samples. Please refer to Footnotes.
- Additional assessments may be carried out at any point in the study where clinically indicated.

**Footnotes:**

- 1 A pregnancy test is required within 3 days prior to C1D1. A negative pregnancy test may be confirmed by urine or blood test. Where a urine test is positive or equivocal, a blood test must be performed to confirm the result. Patients requiring confirmation of post-menopausal status will have FSH and oestradiol levels assessed at Screening. Where applicable, and in accordance with local regulations, a pregnancy test should be conducted at each cycle (or monthly).
- 2 Vital signs will include temperature, systolic blood pressure, diastolic blood pressure, heart rate and respiratory rate. On pembrolizumab dosing days, vital signs will be taken both pre-dose and at the end of infusion.
- 3 Physical examination includes height at Screening and weight at Screening and the start of each cycle. After Screening, further assessments may be symptom-directed.
- 4 Coagulation parameters may be assessed from the Hematology sample.
- 5 Thyroid function testing may be assessed from the Clinical chemistry sample.
- 6 For each ECG assessment, triplicate 12-lead ECGs must be taken less than 5 minutes apart, with the patient having rested for at least 10 minutes in the supine position prior to assessment. Time points are relative to BGB324 dosing: C1 D1 pre-dose and 6 hours after dose; D2 pre-dose; D3 pre-dose; D4 pre-dose. All other time-points are pre-dose unless clinically indicated. If a patient permanently discontinues BGB324 (but continues pembrolizumab), the last ECG will be performed at the next pembrolizumab administration. If a patient has BGB324 interrupted for 14 days for toxicity or QTC prolongation, an ECG will be conducted twice weekly for the following 2 weeks once a patient restarts BGB324 daily dosing.
- 7 Tumor imaging will be performed at Screening, then every 9 weeks for the first 46 weeks, and then every 12 weeks thereafter (+/- 7 days). A tumor response or disease progression should be confirmed no less than 28 days after the initial finding. If treatment administration is misaligned with weeks (e.g. because of treatment delay), the tumor imaging schedule should be maintained by week number and continue if necessary. The schedule of disease assessments is every 12 weeks once a patient has stopped (one or both study treatments) or completed their treatment in the absence of progression. These may continue into Follow Up.
- 8 Fresh tumor tissue from all patients at Screening is mandatory, and optional at up to 2 time points during participation in the clinical trial ('on-study' biopsy). Where possible, these optional samples should be taken at the point of tumor response or progression. Suitable archival biopsy material may also be obtained at Screening. Please refer to protocol [Section 5.3.13](#), the Laboratory or Pathology Manual for full details on biopsy sample collection, time-points, processing, storage and shipment. If a patient discontinues BGB324 (but continues pembrolizumab), there is no requirement for the optional 'on study' biopsy.
- 9 Blood samples will be collected at Screening (or D1 pre-dose), D4, D8, then at every study visit up to and including C9 D1 to prepare PBMC and serum samples for Axl signaling and inhibition biomarker assessment. Please refer to the Laboratory Manual for full details on biomarker sample collection, time-points, processing, storage and shipment. If a patient discontinues BGB324 (but continues pembrolizumab), there is no requirement for biomarker blood samples.
- 10 Pembrolizumab dose of 200 mg will be administered every 3 weeks (timing window +/- 3 days). Each dose will be infused over 30 minutes (timing window -5/+10 minutes)
- 11 BGB324 will be taken orally once daily. On visits when pembrolizumab and BGB324 are given on the same day, pembrolizumab must be given first and the patient observed for 1 h prior to administration of BGB324.
- 12 a) The maximum PK sampling time points for the measurement of BGB324 in blood will be: C1 D1 pre-dose, 2, 4, 6, 8 hours ; D2 pre-dose; D3 pre-dose, 2, 4, 6, 8 hours; D4 pre-dose; and then pre-dose at C1D8, C1D15, C2D1 and then C3D1. Samples should be taken contemporaneously with the ECG assessments on C1 D1-4. All sample times are approximate but every effort must be made to take PK samples at specified times.

- b) The maximum PK sampling time points for the measurement of pembrolizumab in blood will be: C1 D1 pre-dose; D2; D3; D4; and then at C1D8, C1D15; C2D1 pre-pembro dose and then C3D1 pre-pembro dose. All sample times are approximate but every effort must be made to take PK samples at specified times
- c) All sample times are approximate and every effort must be made to take PK samples at specified times. Actual sampling times must be recorded in order to assess result relative to BGB324 or pembrolizumab dose. Please refer to the local Laboratory Manual for full details on PK sample collection, time-points, processing, storage and shipment.
- 13 D1 of next cycle would be "D22" of the previous cycle.
- 14 A Post Treatment Visit is to be conducted up to 30 days (+/-3 days) from last dose of study drugs. Adverse events and concomitant medications must be assessed to 30 days. Some AEs must be assessed for longer (see [Section 7.4.3](#) and [Section 7.5](#)). Other assessments may be carried out between 7-30 days from last dose. Tumor imaging and disease assessment is only required where is part of next scheduled assessment (where patient has not yet progressed) or to confirm response or progression.
- 15 Tumor imaging and disease assessment will continue every 12 weeks from the last dose of study drug where the patient has not yet progressed or to confirm response or progression. An assessment of disease status, survival status and details of any anti-cancer therapies received after last dose of study drug will also be collected. Survival status (every 12 weeks) can be collected by telephone.
- 16 Echocardiogram (or MUGA) will be conducted every 6 months whilst a patient receives BGB324. If a patient discontinues BGB324 (but continues pembrolizumab), a final echocardiogram (or MUGA) will be conducted only if one is scheduled in the following 6 weeks.
- 17 Demography – race, ethnicity, gender, age (birth month and year).
- 18 Hematology and Clinical Chemistry to be assessed at a suitable time prior to administration of study treatment(s).

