### 5.3.9 Electrocardiogram

A resting 12-lead ECG will be performed at the times given Schedule of Study Assessment [Table 4](#) and [Table 5](#). Each assessment time point must be performed in triplicate.

All 12-lead ECGs should be recorded while the patient is in the supine position. ECGs will be recorded at 25 mm/sec. All efforts should be made to ensure that an identical ECG machine is used to collect traces for individual patients. The Investigator or designated physician will review the ECG results.

If any clinically significant findings are observed on the ECG, the Investigator will record it as part of the medical history prior to the start of dosing, and as an AE post dose where the finding represents a change from baseline. Clinically significant findings identified prior to start of dosing must be checked against the study exclusion criteria ([Section 3.2](#)). Note that the average value of the three assessments performed at each time point should be applied, except at Screening, where both the Screening and pre-dose Cycle 1 Day 1 assessments should be combined. Patients may be excluded based on the initial triplicate assessment at Screening.

Patients who discontinue BGB324, but continue with monotherapy pembrolizumab will stop undergoing an ECG.

Patients who have a BGB324 interruption of 14 days for toxicity (see [Table 12](#) and [Table 13](#)) will require an ECG twice weekly for the 2 weeks following recommencement of BGB324 daily dosing. This is to ensure cardiac safety monitoring whilst BGB324 returns to steady state.

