### 6.6.1 BGB324 dose modification for toxicity

If a patient experiences drug related toxicity that requires treatment with BGB324 to be interrupted, a delay of up to 14 days is permitted to allow for resolution of toxicity. In the absence of recovery, treatment with BGB324 should be discontinued. See [Table 12](#).

If treatment with BGB324 is interrupted, the relevant toxicity must have resolved to  $\leq$ Grade 1 or tolerable Grade 2 or baseline for treatment to recommence.

Only one dose reduction from 200 mg to 100 mg daily dose is possible.

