**Table 12: Dose Modification for BGB324-related Toxicity**

Grade (CTCAE)		Recommended Dose Modification
Grade 1 and Grade 2 (tolerable)		
Any occurrence		Maintain dose of 200 mg if toxicity is tolerated by the patient
Grade 2 (intolerable)		
1 st or 2 nd occurrence of same adverse event		Interrupt treatment until toxicity returns to baseline, Grade 1 or tolerable Grade 2 Resume dosing at 200 mg
3 rd occurrence of same adverse event		Interrupt treatment until toxicity returns to baseline, Grade 1 or tolerable Grade 2 Dose reduce to 100 mg
4th occurrence of same adverse event		Discontinue permanently
Grade 3		
1 st occurrence		Interrupt treatment until toxicity returns to baseline, Grade 1 or tolerable Grade 2 Dose reduce to 100 mg or Discontinue permanently if dose has already been reduced
2 nd occurrence of same adverse event at G3		Discontinue permanently
Grade 4		
1 st occurrence		Discontinue permanently
Notes:		

 
Treatment interruption for BGB324-related toxicity should be limited to 14 days
 
Dose reduction below 100 mg daily is not possible (a single capsule contains 100 mg BGB324)
 
Patients being considered for dose reduction or permanent discontinuation of BGB324, may be discussed with
 
		

Grade (CTCAE)	Recommended Dose Modification
the Medical Monitor	
• Patients require an ECG twice weekly for the first 2 weeks after recommencing BGB324 following an interruption (see Section 5.3.9 )	

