**Table 13: Dose modification of BGB324 for QTc Prolongation**

QTcF	Recommended BGB324 Dose Modification
Grade 1 (450-480 ms)	
Any occurrence	No dose modification required
Grade 2 (481-500 ms) - on two consecutive occasions per protocol assessments or investigator's judgement	
1 st occurrence	Interrupt treatment with BGB324: i) if QTcF reduces to $\leq$ Grade 1 by 14 days from initial recording, restart BGB324 at a reduced dose of 100mg or discontinue if no further dose reduction is possible. ii) if QTcF does not reduce to $\leq$ Grade 1 by 14 days from initial recording, discontinue BGB324 permanently.
$\geq$ 2 nd occurrence (following a previous dose reduction for QTcF)	Discontinue BGB324 permanently.
$\geq$ Grade 3 ( $\geq$ 501 ms)	
1 st occurrence	Interrupt treatment with BGB324: - if QTcF reduces to $\leq$ Grade 1 by 14 days from initial recording, restart BGB324 at a reduced dose of 100mg or discontinue treatment if dose reduction is not possible - if QTcF does not reduce to $\leq$ Grade 1, discontinue BGB324 permanently.
2 nd occurrence	Discontinue BGB324 permanently
Ventricular arrhythmia	
1 st occurrence	Discontinue BGB324 permanently
Notes:	
• Serum calcium, magnesium and potassium should be measured regularly whilst receiving BGB324; all abnormal results should be corrected	
• The mean QTcF value from triplicate ECG readings should be used when considering dose modification	

QTcF	Recommended BGB324 Dose Modification
	

• Treatment interruption for BGB324-related toxicity should be limited to 14 days

• Dose reduction below 100 mg daily is not possible (a single capsule contains 100 mg BGB324)

• Patients being considered for dose reduction or permanent discontinuation of BGB324 may be discussed with the Medical Monitor

• Patients require an ECG twice weekly for the first 2 weeks after recommencing BGB324 following an interruption (see Section 5.3.9)

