## 6.8 Permitted and Restricted Concomitant Medications

In general, medications or vaccinations specifically prohibited in the exclusion criteria are not allowed during the ongoing trial. Treatment with antacids, proton pump inhibitors and histamine receptor 2 inhibitors can be initiated as rescue therapy after patients have been receiving BGB324 for one week, provided they are taken in the evening.

If there is a clinical indication for any medication or vaccination specifically prohibited during the trial, discontinuation from trial therapy or vaccination may be required. The investigator should discuss any questions regarding this with the Sponsor Clinical Director. The final decision on any supportive therapy or vaccination rests with the investigator and/or the patient's primary physician. However, the decision to continue the patient on trial therapy or vaccination schedule (see [Section 6.10](#)) requires the mutual agreement of the investigator, the Sponsor and the patient.

Patients should not receive BGB324 during periods of systemic corticosteroid treatment. If a patient requires treatment with systemic corticosteroids, BGB324 should be interrupted immediately. Treatment with BGB324 may be restarted upon completion of systemic corticosteroid therapy. BGB324 may be continued at the appropriate dosage during periods of topical and inhaled corticosteroid therapy.

Hormonal contraception for female breast cancer patients is contraindicated.

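### The twice-weekly ECGs after restarting BGB324 have two different triggers: an interruption of 14 days in footnote 6 and Section 5.3.9, an interruption of any length in the notes to Tables 12 and 13

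*Protocol*

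**What the plan says.** Four places in the protocol set the rule for ECGs after BGB324 is restarted.

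- Schedule of assessments, footnote 6: "If a patient has BGB324 interrupted for 14 days for toxicity or QTC prolongation, an ECG will be conducted twice weekly". The ECGs run for the 2 weeks after daily dosing resumes.
- Section 5.3.9: "Patients who have a BGB324 interruption of 14 days for toxicity" need the same ECGs, with a pointer to Tables 12 and 13. The stated purpose is: "This is to ensure cardiac safety monitoring whilst BGB324 returns to steady state".
- Notes to Table 12 (BGB324-related toxicity): "Patients require an ECG twice weekly for the first 2 weeks after recommencing BGB324 following an interruption", with a pointer back to Section 5.3.9.
- Notes to Table 13 (QTc prolongation): the same sentence and the same pointer.

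The length of a hold is limited elsewhere. In Section 6.6.1, "a delay of up to 14 days is permitted to allow for resolution of toxicity". The notes to both tables add: "Treatment interruption for BGB324-related toxicity should be limited to 14 days". For QTc prolongation, Table 13 makes the restart depend on QTcF falling to Grade 1 or lower "by 14 days from initial recording, restart BGB324 at a reduced dose of 100mg".

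**The concern.** The passages agree on the frequency and duration of the ECGs, but not on which patients get them. Two of them name a 14-day interruption. The other two name an interruption without qualification. Because 14 days is the most that a toxicity hold may last, the difference concerns every hold that ends before the limit.

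Section 6.6.2 states that BGB324 produces QTc prolongation, and Table 13 bases dose reduction and permanent discontinuation on QTcF readings after restart. If sites follow different passages, patients with the same hold will have different numbers of ECGs in the fortnight after re-exposure. ECGs are among the secondary safety assessments in Table 9, so how intensively they are collected should not depend on which page a site consulted.

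**Working it through.** The protocol gives no figure to reproduce. The check compares the passages and counts ECG time points.

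**1. The triggers side by side**

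| Place | Length of interruption | Reason |
|---|---|---|
| Footnote 6 | 14 days | toxicity or QTc prolongation |
| Section 5.3.9 | 14 days | toxicity, citing Tables 12 and 13 |
| Table 12 notes | none stated | table covers BGB324-related toxicity |
| Table 13 notes | none stated | table covers QTc prolongation |

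**2. Do the cross-references settle it?** The table notes cite Section 5.3.9, and Section 5.3.9 cites the tables. Neither is said to prevail, so a reader who follows the pointers returns to the starting point.

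**3. Who is affected?** A hold for toxicity may last 1 to 14 days (Section 6.6.1, Tables 12 and 13). A literal 14-day trigger is met only at the upper limit. Holds of 1 to 13 days meet the trigger in the tables and not the one in footnote 6 and Section 5.3.9.

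**4. ECG time points in the 2 weeks after restart, hold of 1 to 13 days**

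- Tables 12 and 13: 2 per week × 2 weeks = 4 additional time points, each in triplicate.
- Footnote 6 and Section 5.3.9, read literally: 0 additional time points.
- Routine ECGs: from Cycle 2, visits are 3 weeks (21 days) apart. A 14-day window therefore contains 0 or 1 routine ECG, and the next one can fall up to about 3 weeks after restart.

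**5. Related restarts.** Section 6.6 sends diarrhea, rash and renal toxicity to Section 6.6.4. Tables 15 to 17 there also withhold BGB324 for up to 14 days and then restart it, but carry no ECG note. Footnote 6 speaks of toxicity in general and could include these restarts. The notes to Tables 12 and 13 do not clearly reach them.

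**The case against.** The strongest reply is that the passages can all be obeyed together. Footnote 6 and Section 5.3.9 do not say that ECGs follow only a 14-day interruption, so a site that does them after a 5-day hold breaches nothing. Because 14 days is the cap and Section 5.3.9 cites the tables, its wording may have been meant as shorthand for the hold that those tables allow. An investigator deciding on a restart after QTc prolongation must also consult Table 13, which carries the ECG requirement.

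This reading is possible, but the text does not establish it. The table notes state a complete requirement without a 14-day condition. A site that relies on footnote 6 alone can omit ECGs that the tables require.

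Other safeguards limit the harm:

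- Restart after a QTc hold requires QTcF to have fallen to Grade 1 or lower.
- An average QTc of 480 ms or more calls for close monitoring until it falls below 480 ms.
- ECGs continue at scheduled visits, and extra assessments are allowed when clinically indicated.

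A reader might infer that a recurrence of QTc prolongation would go unseen. With these safeguards that is a worst case, and the documents do not support it as the expected result.

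It is also fair to say that little in the planned analysis turns on this. Section 8.12.1.4 plans only listings of ECG data. That limits the statistical weight of the point but does not remove the contradiction in a monitoring rule.

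**Conclusion.** The inconsistency stands and is in the current text. For any toxicity or QTc hold that ends before day 14, the requirement is 4 additional ECG time points under Tables 12 and 13 and none under a literal reading of footnote 6 and Section 5.3.9. The primary response-rate analysis and the two-stage decision rules are unaffected. The effect is on cardiac safety monitoring and on how evenly ECG data are collected. The point rests on reading the 14 days as a required length, which is what the words say.

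Three stronger readings are tempting and should not be drawn.

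- **That most restarted patients are affected.** The protocol gives no distribution of hold lengths. If restart days were spread evenly over days 1 to 14, the share would be 13/14 = 93%, but that is an assumption; the possible range is 0% to 100%.
- **That the rule matters most for holds during systemic corticosteroids.** Section 6.8 says "Treatment with BGB324 may be restarted upon completion of systemic corticosteroid therapy" and does not mention restart ECGs. No passage contradicts another here. Footnote 6 does not restrict toxicity to BGB324-related events, so some of these holds may already fall under it. Where monitoring is most needed is a clinical judgement.
- **That footnote 6 can never apply to a Grade 2 QTc event**, because the 14 days in Table 13 run from the initial recording and Grade 2 normally needs two consecutive findings. The table does not say which recording starts the clock, so this cannot be settled from the text.

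**What to change.** Reconcile footnote 6, Section 5.3.9 and the notes to Tables 12 and 13 so that one trigger, stating the length of and reason for the interruption, appears in the same words in all four places. The sponsor's medical team must choose the trigger; this review takes no position on it. The same change should say whether the trigger also applies when BGB324 is restarted under Tables 15 to 17.

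The cost is one harmonised sentence in four places and one clarification for Tables 15 to 17. If the wording of Tables 12 and 13 is kept for the restarts they govern, no ECGs are added beyond those the tables already require. If the trigger is extended to restarts under Tables 15 to 17, the addition is at most 2 × 2 = 4 time points per restart.
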